5.6 Sampling frame

The sample frame is made up of all persons over 18 years of age who attended health service provider institutions (IPS) participating in the study in hospitalization, emergency, outpatient, and any other hospital care services.

5.7 Sample selection method

Non-probabilistic convenience sampling will include all patients who meet the eligibility criteria. The inclusion of participants will be consecutive until the calculated sample size is completed.

5.8 Sample size

Considering that the prevalence of HCV in the hospital population with risk factors is unknown, 50% will be considered, with a confidence level of 95%, an error of 5%, a design effect of 3, and a population served on average for the institutions included of 280,186 during 2021, the minimum sample size required per institution is 1,151 and the maximum with a confidence level of 99.99% is 4,519 (Table 1).

Table 1. Sample size for frequency in a population

Population size (for finite population correction factor or fcp)(N):	280.186
Hypothetical % frequency of the outcome factor in the population (p):	50%+/-5
Confidence limits as % of 100(absolute +/-%)(d):	5%
Design effect (for group surveys-EDFF):	3

Sample Size (n) for Various Confidence Levels	
Confidence Interval (%)	Sample size
95%	1151
80%	493
90%	811
97%	1411
99%	1986
99.90%	3236
99.99%	4519

Sample size $n = [EDFF * Np(1-p)] / [(d^2 / Z^2(1-\alpha/2)^2 * (N-1) + p*(1-p)]$.

Source: Results from OpenEpi, version 3, the SSPropor open-source calculator.

5.9 Sampling and data collection procedure

Once approval for the present study has been obtained from the research ethics committee, the standardized data collection phase will begin. Search strategy through opportunity screening. For each person who meets the inclusion criteria and wishes to participate, informed consent will be requested and a data collection form will be filled out (Annex 1). These patients will undergo pre-test counseling, a presumptive rapid test for HCV, and if positive, contact information will be requested for post-test counseling and evaluation through teleconsultation by one of the principal investigating hepatologists who will guide them to access the confirmatory test for HCV, the study will assume the responsibility for its realization. Once the care pathway is established, the subsequent follow-up of the patient with a reactive hepatitis C antibody test will be done through their EAPB or EOC.

The sample will be taken by trained personnel by capillary puncture of the thumb region of the fingers of the right hand, after asepsis and antisepsis, the rapid diagnostic test HCV Ab Plus Rapid test with INVIMA registration 2018RD-0002353-R1 will be used with operational characteristics that allow its performance at the point of care obtaining a result in 15 to 20 minutes. This rapid test for antibodies against HCV may be replaced by another test with similar operational characteristics (sensitivity and specificity). The recommendations described by the test manufacturer should be followed.

Once the capillary blood sampling is performed, the used implements and the blood samples obtained will be discarded according to biosafety protocols and no additional studies will be performed with these samples. The spaces designed to dispose of the material used will be the guardian to dispose of sharps and items contaminated with blood in a red biohazard bag that will go to final disposal by the company in charge of this purpose in the institution where the sample collection is carried out.

Cases with reactive hepatitis C antibody tests will be reported to the hepatologist, gastroenterologist, or infectologist linked to the institution and who acts as the leading physician of the strategy in each institution and to the epidemiology service or unit of the respective institution for follow-up and notification to the National Public Health Surveillance System - SIVIGILA.

Performing hepatitis C viral load for cases with positive hepatitis C antibodies either through a reference laboratory (Colcan) with which ACH has established an agreement or by payment to the Clinical Laboratory of the Hospital.

All the information obtained will be recorded and processed individually (case by case) through a digital information system with cloud backup in real-time using a Case Report Form (CRF), with the use of a tablet. The review and validation of the data capture will be performed weekly. The information will be guarded and encrypted for the exclusive use of the principal investigators belonging to the Colombian Association of Hepatology, periodic quarterly reports and a final report will be submitted to each of the participating institutions. The information will be anonymized for their use. Access to the information will be independent for each institution.

5.10 Data Analysis Plan

Descriptive analysis will be performed for all variables of interest proposed in this study. Descriptive statistics (frequencies and percentages) will be estimated. For continuous quantitative variables, measures of central tendency (mean and median) and measures of dispersion (variance, standard deviation) will be estimated. Possible relationships between sociodemographic variables, risk factors, and documentation of positive HCV antibodies will be explored, for which a bivariate analysis will be performed using X² (chi-square) tests to explore the proposed associations. All analyses will be performed with Stata version 18.

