4.1 General objective

To determine the prevalence of HCV in patients with risk factors for HCV captured through opportunity screening in the hospital institutions included.

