4.2 Specific objectives

- Characterize the study population socio-demographically.
- Describe the epidemiological characteristics of HCV antibody-positive patients.

- Determine the proportion of patients with positive HCV antibodies and positive viral load (quantitative) for HCV.
- Perform an exploratory analysis of the association of positive cases and the different risk factors for HCV infection.
- Quantify how many HCV-positive individuals were able to access the management pathway and treatment.

5 Methodology

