5.5 Variables

Table 1. Study variables

Category	Variable name	Conceptual definition	Operational definition	Measuring scale
Sociodemographic	ID Number	ID Number	Personal identification number under which you are registered in the country of origin	Nominal
	Age	Duration of an individual's existence measured in units of time.	Number in years	Continual
	Gender	Categorizes the	1. Female	Nominal

Category	Variable name	Conceptual definition	Operational definition	Measuring scale
		individual according to her biological characteristics.	0. Male 2. Undetermined	
	Nationality	Country of birth	Name of country	Nominal
	Department of Residence	A geographic place to which the municipality or city where the person usually resides belongs.	Name of department	Nominal
	Municipality of residence	Geographic place municipality/city where the person usually resides.	Name of municipality/city	Nominal
	Health Service Provider Institution (IPS)	Place where the screening was performed.	1= Fundación cardioinfantil 2= Fundación Santafé 3= Clínica Colombia 4= Hospital Universitario San Ignacio 5= Fundación Valle de Lili 6= Hospital Pablo Tobón Uribe 7= Hospital Universitario Julio Méndez Barreneche E.S.E.	Nominal, polytomous
	Affiliation regime	Category of affiliation to the health system.	0=Not insured 1=Subsidized 2=Contributory 3=Special 4=Exception	Nominal, polytomous
	Entity Benefit plan administrator (EAPB) or Entity obliged to compensate (EOC)	The entity in charge of health care coverage.	Name of entity	Nominal
Risk Factors	Transfusion of blood products	Administration of hemocomponents before 1996.	0. No 1. Yes	Nominal, dichotomous

Category	Variable name	Conceptual definition	Operational definition	Measuring scale
	The year in which you received the transfusion	Date (year) in which you received the transfusion.	The year in which you received the transfusion	Continual
	Major surgery	Surgical procedure performed in the operating room under general or regional sedation that may require post-procedural in-hospital monitoring.	Abdominal laparotomy: 0. no; 1 Yes Gynecologic surgery of any type: 0. No; 1 Yes Orthopedic surgery of any type: 0. No; 1 Yes Any surgery that required in-hospital post-procedure surveillance for more than 24 hours: 0. 0. No; 1 Yes	Nominal, dichotomous
	Intravenous drug use	Having consumed intravenous drugs at any time.	0. No 1. Yes	Nominal, dichotomous

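### Section 5.10 names no 95% interval for the prevalence and does not say how hospital or the design effect of 3 enters the analysis, although section 5.8 sizes each institution for such an interval.

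*Combined protocol and SAP*

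**What the plan says.** The general objective (4.1) is the prevalence of HCV in at-risk patients "captured through opportunity screening in the hospital institutions included". Section 5.8 sets 95% confidence, 5% absolute error, 50% prevalence and a design effect of 3, and concludes that "the minimum sample size required per institution is 1,151 and the maximum with a confidence level of 99.99% is 4,519". The only description of the 3 is the calculator's row label, "Design effect (for group surveys-EDFF"; the groups are not named.

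Section 5.10 says: "Descriptive statistics (frequencies and percentages) will be estimated". It adds means, medians, variances and standard deviations. Sociodemographic variables and risk factors are related to antibody positivity by bivariate "chi-square) tests to explore the proposed associations". In the text available, no section names a confidence interval for the prevalence, a use for the design effect, or stratification by hospital.

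Two other places bear on this. The variable list in 5.5 records the institution ("Place where the screening was performed") for all seven hospitals. Section 5.9 promises each institution its own quarterly and final reports, and adds: "Access to the information will be independent for each institution".

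**The concern.** The sample size rests on the width of an interval that the analysis plan never commits to reporting. The study's main result could therefore appear as a bare percentage. Because each hospital receives its own reports, hospital-level percentages are likely to be read as well (an inference), and at low prevalence each would rest on a handful of positives. The ±5 points calculated at 50% does not convey that uncertainty.

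The second part concerns the specific objective in 4.2: "Perform an exploratory analysis of the association of positive cases and the different risk factors for HCV infection". A two-by-two chi-square of factor against antibody result, with no stratum named, compares people across hospitals as if hospital did not matter. If prevalence and the frequency of a factor both differ between hospitals, that difference alone can create an association or hide one. Hospital is already recorded, so this source of confounding can be removed.

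**Working it through.** **1. The plan's own figure.** Inputs from 5.8: N = 280,186, p = 0.5, d = 0.05, z = 1.96, DEFF = 3.

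n = DEFF × N p(1−p) / [(d²/z²)(N−1) + p(1−p)]

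- Numerator without DEFF: 280,186 × 0.25 = 70,046.5.
- Denominator: (0.0025/3.8415) × 280,185 + 0.25 = 182.6.
- DEFF 1: 383.6. DEFF 3: 1,150.9, so 1,151.

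The figure reproduces. The design effect triples the size per institution. At 50% and n = 1,151, the half-width is ±5.0 points with DEFF 3 and 1.96 × √(0.25/1,151) = ±2.9 points without it. The ratio is √3 = 1.73.

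**2. The missing interval at low prevalence.** The only local prevalence figures are for general populations (section 1: 0.67% for Colombia, under 1% for Latin America). Section 2 expects more with targeted screening, so a range is shown. Every prevalence in the table is an assumption about this study. The Wilson limits are

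[p + z²/2n ± z√(p(1−p)/n + z²/4n²)] / (1 + z²/n)

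with n = 1,151, or the effective size 1,151/3 = 383.7.

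| Assumed prevalence | Positives in 1,151 | 95% interval, n = 1,151 | 95% interval, n = 383.7 |
|---|---|---|---|
| 0.67% | about 8 | 0.34–1.33% | 0.21–2.11% |
| 1% | about 12 | 0.57–1.76% | 0.38–2.59% |
| 2% | about 23 | 1.34–2.98% | 1.00–3.95% |
| 5% | about 58 | 3.88–6.42% | 3.23–7.66% |

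At 0.67% the limits in one hospital differ almost fourfold (1.33/0.34 = 3.9). If all seven hospitals reach the minimum (7 × 1,151 = 8,057, a total the documents do not state), the overall interval at 0.67% is 0.51–0.87% without a design effect.

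**3. The risk-factor tests.** The documents give no hospital-level prevalence or factor frequency, so this step is simulation under assumed spreads: seven hospitals of 1,151, mean prevalence 1%, a factor carried by 20% on average, two-sided 5% tests. It compares the crude chi-square with the hospital-stratified Mantel-Haenszel test when the true odds ratio is 1.

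| Spread between hospitals | Crude, random matching | Crude, perfect alignment | Stratified |
|---|---|---|---|
| None | about 5% | about 5% | about 5% |
| Prevalence 0.67–1.33%, factor 10–30% | about 5% | about 7% | about 5% |
| Prevalence 0.4–1.6%, factor 5–35% | 6–7% | about 16% | about 5% |

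Perfect alignment means that the hospital with the highest prevalence also has the highest factor frequency, and so on down the ranking. It is a worst case. With a true odds ratio of 2, the widest spreads and random matching, power is about 71% crude against 76% stratified. With no hospital differences, power is 80% for both, so stratifying loses nothing.

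**The case against.** Several points on the other side stand.

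- **Pooling is not stated.** A reader might infer that 5.10 pools its chi-square tests over the seven hospitals. It does not say so. Because 5.8 sizes each institution and 5.9 reports to each, tests run hospital by hospital remain possible. Section 5.10 is silent, and ignoring hospital is only the plain reading of an unstratified bivariate test. Hospital may itself be cross-tabulated with the antibody result, but that would not adjust the factor tests.
- **The large simulated errors are extremes.** The 16% needs perfect rank alignment across hospitals. Under random matching the excess is at most about two points. One factor could be badly aligned, but nothing in the documents shows that any is.
- **The tests are exploratory** in a descriptive study, and no decision is tied to a p-value. Stratifying by hospital also leaves other confounding, for example by age, since eligibility changes at 50.
- **An interval can be computed later** from reported counts, so no data are lost. Convenience sampling limits what any interval means.

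Two further readings are tempting and unsupported. One is that the sample is too small: ±5 points at 50% is a valid bound, and nothing shows a shortfall. The other is that the 3 measures clustering between hospitals, so that a simple overall interval would be 1.73 times too narrow. The 3 is applied inside each institution's calculation, and the documents do not say what it represents.

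None of this answers the main gap. A plan sized wholly on a confidence interval should commit to reporting one.

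**Conclusion.** The point holds in two parts of unequal weight.

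The firmer part is the prevalence. The size calculation reproduces and depends only on a 95% interval, and 5.10 names none. At the low prevalences in the table, one hospital's percentage would carry limits such as 0.34–1.33% that a bare percentage hides. Whether those limits should widen to 0.21–2.11% depends on the meaning of the design effect, which is open.

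The weaker part is the risk-factor analysis. If the tests ignore hospital, they are open to confounding by hospital, but its size is unknown. Under the assumed spreads the crude false-positive rate is about 5–7% with random matching and about 7–16% in the worst case, while the stratified test stays near 5%. The argument for stratifying is that it costs almost nothing, not that serious error has been shown.

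Confidence is moderate.

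**What to change.** Both changes are to section 5.10.

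1. **Prevalence.** Report antibody-reactive and viral-load-positive prevalence, each with everyone screened as the denominator, overall and for each hospital, with Wilson or exact 95% intervals. If the sponsor confirms that the design effect of 3 reflects real clustering within a hospital, compute the intervals from the effective sample size (n/3).
2. **Risk factors.** Replace the crude chi-square tests of risk factors with Mantel-Haenszel tests and odds ratios stratified by hospital, still labelled exploratory. Use an exact stratified version when few exposed positives are expected. As a guide, with 8,057 screened at 0.67% there are 8,057 × 0.0067 = 54 positives, so fewer than 5 exposed positives are expected for any factor carried by under 5/54 = 9.3% of participants.

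The cost is a few sentences and standard Stata commands on data already collected, with no extra patients. The downsides are slightly more analysis and precision that looks less favourable at low prevalence. Neither change corrects for convenience sampling or for other confounders such as age.

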Chronic HCV infection can remain asymptomatic until the late stages, leading to low awareness of the patient's infection status and a significant proportion of undiagnosed individuals (21). HCV infection is diagnosed in two stages: a. Detection of anti-HCV antibodies with a serological test reveals infection. b. If the test is positive for anti-HCV antibodies, a nucleic acid test for HCV ribonucleic acid (RNA) (viral load) is needed to confirm chronic infection and the need for treatment (2).

A study presented at the American Association for the Study of Liver Diseases (AASLD) Annual Meeting has concluded that the prevalence of viremic hepatitis C virus (HCV) infections declined from 66 million in early 2015 to 59 million in early 2020 (22); hepatitis C is a curable disease that if not diagnosed and treated on time can progress to liver cirrhosis, hepatocellular carcinoma, and death related to these and other hepatic or extrahepatic problems (20). The worldwide prevalence of HCV infection is estimated to be 0.75% (95% CI 0.6-0.8%) in the early 2020s (22).

Researchers at the Center for Disease Analysis Foundation (CDA) estimated from 2015 to 2019 7.5 million new chronic HCV infections, 1.3 million newly diagnosed that year (22). By 2019, of the 59 million HCV-infected persons worldwide, an estimated 21% (15.2 million) were diagnosed and, by the end of 2019, 9.4 million had been treated with Direct-Acting Antivirals (DAAs) (62% of persons diagnosed with chronic HCV infection), 8.8 million infections cured, and 5.5 million all-cause and liver-related deaths (2, 22).

Globally, more than three-quarters of HCV viremic infections remained undiagnosed at the beginning of 2020, and more than 90% of people with active hepatitis C remained untreated with DAAs. In high-income countries in 2020, ADC researchers estimated that 6 million people had a viral infection, of whom 47% had been diagnosed and 11% of those diagnosed were receiving treatment. The percentage of people with active hepatitis C is estimated to be 27% in upper-middle-income countries, 15% in lower-middle-income countries, and 16% in low-income countries. As for the percentage of people diagnosed and treated with DAAs, it is 3 % in upper-middle-income countries, 4 % in lower-middle-income countries, and 4 % in low-income countries (23).

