the high-cost account (including those in the 2017-2018 cohort). Of the 634 users enrolled in the 2019 cohort, 584 initiated treatments, of which 97.6% (570) did so with centrally purchased drugs. Of the 326 cases included in the 2020 cohort, 219 initiated treatments, 98.6% (216) with centrally purchased drugs, which made evident the almost exclusive use of the strategy, except in cases of stage 4-5 chronic kidney disease. Of the 1,142 patients reported to the CAC in 2017 and 2018, 1,079 had initiated treatment and of these 84.2% (n=909), were included in the centralized purchasing model, the most frequently used treatment in 98.2% of cases in the 2019-2020-2021 cohort was sofosbuvir/velpatasvir, reaching 98.77 in 2021 (12).

Regarding the effectiveness of the treatment, it was found that for the 2017-2018 cohort, with centrally purchased drugs, the effectiveness was 95.1% and with drugs outside the centralized purchasing model it was 96.4%. For the 2019 cohort, the effectiveness was 98% and 100% respectively. In the 2020 cohort, treatment effectiveness is at 100% (12).

The report concludes that there is high effectiveness of direct-acting antiviral treatments (greater than 95%), follow-up is observed in the application of the clinical route and practically exclusive use of drugs included in the centralized purchasing model; however, there is a need to encourage screening in the population over 50 years of age and according to risk exposure, as established in resolution 3280 of 2018 (12).

3 Research question

What is the prevalence of HCV in the population with risk factors for hepatitis C virus infection captured by screening with rapid tests in health care institutions in Colombia?

4 Objectives

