5.3 Inclusion criteria

Have at least one of the following risk factors for hepatitis C.

- Over 50 years of age with no risk factors.
- Over 18 years old and < 50 years old, with risk factors for hepatitis C:
 - ✓ Persons who have received medical or dental interventions in health care settings.
 - ✓ Persons who have had tattoos, body piercings, or scarification procedures.
 - ✓ Persons with HIV or hepatitis B infection.
 - ✓ Persons who inject drugs.
 - ✓ Persons who have used intranasal drugs.
 - ✓ Persons deprived of liberty and previously incarcerated persons.
 - ✓ Anyone with abnormal liver tests or liver disease.
 - ✓ Students, health care workers, or members of public safety (e.g. correctional

service officers or police) who have come into contact with blood at work through needlestick or sharps injuries.

- ✓ Anyone who has undergone hemodialysis.
- ✓ Persons who received transfusions in Colombia before 1996.
- ✓ Persons with comorbidities potentially associated with CH: diabetes, ischemic heart disease, cryoglobulinemia, chronic renal failure, Sjögren's syndrome, hypothyroidism, lichen planus, rheumatoid arthritis, HIV, non-Hodgkin's lymphoma, acute lymphoblastic leukemia, waldenstrom's macroglobulinemia.
- Individuals previously treated for HCV with sustained viral response in whom reinfection is suspected (individuals who continue to engage in risk behaviors)
- Accept to participate in the study by signing the informed consent form.

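### Risk-factor associations rest on unadjusted chi-square tests alone, with no effect measure, interval or age-adjusted result, although few positives are likely

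*Combined protocol and SAP*

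**What the plan says.** Section 5.10 is the whole analysis plan. After counts, percentages and summary statistics, it deals with associations in one sentence: "Possible relationships between sociodemographic variables, risk factors, and documentation of positive HCV antibodies will be explored, for which a bivariate analysis will be performed", using "chi-square) tests to explore the proposed associations". No section names a regression, a stratified analysis, an odds or prevalence ratio, or an interval for any estimate. The 95% level in section 5.8 belongs to the sample size calculation.

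Section 4.2 labels the association objective exploratory, and section 5.1 calls the study descriptive and cross-sectional.

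Eligibility in section 5.3 differs by age. One route is "Over 50 years of age with no risk factors"; the other is "Over 18 years old and < 50 years old, with risk factors for hepatitis C", followed by the list of factors. Age in years is collected (section 5.5 and Annex 1).

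**The concern.** There are two separate issues.

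- **No size or precision.** A chi-square p-value does not say how strong an association is or how well it is estimated. With few positives, a non-significant result may be read as no association when the data are compatible with a halving or a doubling of the odds. This needs no assumption about age.
- **Age may be mixed in.** A factor whose frequency differs by age will show a crude association with positivity whenever positivity also differs by age, even if the factor has no association within age groups. At least one listed factor must differ by age: "Persons who received transfusions in Colombia before 1996". If enrolment is in 2023 or later (the reference list carries 2023 dates), nobody aged 26 or under in 2023 can have that exposure.

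At stake is the reading of the plan's only association tests. The prevalence estimate does not depend on them.

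**Working it through.** **Plan's own figure.** Section 5.8 uses N = 280,186, p = 0.5, d = 0.05 and design effect 3. With z = 1.96, n = 3·N·p(1−p) / [(d²/z²)(N−1) + p(1−p)] = 1,150.9, so 1,151 per institution reproduces. Seven institutions are listed in section 5.5: 7 × 1,151 = 8,057.

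**Expected positives.** Prevalence in this population is unknown. Assume 0.67% (the national figure in the introduction) to 1%: 8,057 × 0.0067 = 54 and 8,057 × 0.01 = 81.

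**Precision.** Take a factor held by 10% (assumed) with a true odds ratio (OR) of 1, participants treated as independent, and SE(log OR) = √(1/a + 1/b + 1/c + 1/d).

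- At 0.67%: a = 5.4 exposed positives, b = 800.3, c = 48.6, d = 7,202.7. SE = 0.455, and exp(±1.96 × 0.455) gives 0.41 to 2.44.
- At 1%: a = 8.1, b = 797.6, c = 72.5, d = 7,178.8. SE = 0.373, giving 0.48 to 2.08.
- One institution alone (1,151) at 0.67%: 7.7 positives, limits 0.09 to 10.6. Hence the pooled analysis.

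**Age distortion, one worked case (all rates assumed).** Half the sample is over 50. Positivity is 1.33% over 50 and 0.67% under 50 (ratio 2, 1% overall). A null factor is held by 10% over 50 and 20% under 50.

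- Exposed positives: 8,057 × (0.5 × 0.10 × 0.01333 + 0.5 × 0.20 × 0.00667) = 10.7. Exposed negatives: 1,197.8.
- Unexposed positives: 69.8. Unexposed negatives: 6,778.6.
- Crude OR = (10.7 × 6,778.6) / (1,197.8 × 69.8) = 0.87, although the OR within each age group is 1.

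**Age distortion, grid.** Share over 50: 30% to 70%. Positivity ratio: 1.5 to 3. Prevalence: 0.67% or 1%. Factor frequency: 20% or 25% in one age group against 5%, 10% or 15% in the other. This makes 240 cells in each direction. Rejection comes from the non-central chi-square at n = 8,057.

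| Null factor | Crude OR, range | Median |
|---|---|---|
| Commoner under 50 | 0.63 to 0.97 | 0.86 |
| Commoner over 50 | 1.03 to 1.58 | 1.15 |

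The 5% test rejects in 5% to 33% of datasets. The median is 7%; 74% of the 480 cells are below 10% and 3% are above 20%. With no age gradient in positivity the OR is 1.00 and rejection is 5%. Wider assumed gaps in frequency (10% against 50%, or 5% against 30%), with positivity 2 to 4 times higher over 50, give a crude OR of 0.51 to 0.73 and rejection of 9% to 79%. The size is therefore set by what is assumed.

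**Pre-1996 transfusion.** Assume frequency 0 at 18 to 26, 1% to 3% at 27 to 49, and 5% to 10% at 50 and over. A null factor shows a crude OR of 1.05 to 1.76 (median 1.22). In about 90% of these cells fewer than 5 exposed positives are expected, so sparse data matter here at least as much as age.

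**What age adjustment does and does not do.** In simulations (2,000 runs per scenario, null factor, eight scenarios with positivity varying by age), the age-adjusted Firth OR was 1.00 to 1.06 with 95% to 96% coverage. Those simulations did not model entry conditional on holding a factor. Suppose that rule binds. Among under-50s, let factor A have OR 10 and frequency 5%, let half hold some other null listed factor, and let baseline positivity be 0.5% (all assumed).

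- Positivity with A: odds 0.005025 × 10 = 0.05025, so 4.785%.
- Holders of a null factor B all qualify: 0.05 × 0.04785 + 0.95 × 0.005 = 0.714%.
- Non-holders of B need A or another factor: (0.05 × 0.04785 + 0.475 × 0.005) / 0.525 = 0.908%.
- OR for B within the under-50s = 0.79. It is 0.89 if 70% hold another factor and 0.99 if 95% do. Age adjustment leaves this in place.

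**The case against.** The strongest reply is that the method suits the aim. The objective is exploratory, the study is descriptive, and nothing in the protocol claims independent or causal risk factors. For case finding, crude positivity by factor is a legitimate target, and a crude table describes the overall association correctly. Percentages by group would also come naturally from the cross-tabulations, so the fair statement is that no effect measure or interval is named, not that the data would be hidden. All of this stands, and it lowers the priority. It does not supply the missing interval.

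A reader might infer that the entry rule in section 5.3 confounds every crude test with age, and that age adjustment would put this right. The documents support neither half.

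- They give no age-specific positivity. Listing the over-50 route under "Have at least one of the following risk factors for hepatitis C", and citing a report that "there is a need to encourage screening in the population over 50 years of age and according to risk exposure", are reasons to expect an age gradient, not evidence of its size.
- The first factor listed for under-50s is medical or dental care in a health care setting, without qualification, in a population of hospital users. Read literally, nearly every younger patient qualifies, and the rule links age to the factors only weakly.
- If the rule does bind, it also selects within the younger group, and adjusting for age does not undo that.

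**Conclusion.** The point holds as a low-priority improvement. Section 5.10 plans only unadjusted chi-square tests and names no effect measure or interval. With about 54 to 81 positives in 8,057 (if prevalence is 0.67% to 1%), a p-value says little. A factor held by 10% would have limits of roughly 0.4 to 2.4, or 0.5 to 2.1, around no association.

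Mixing with age is possible but conditional. It needs positivity to vary with age, which the documents do not establish, and on the main assumed grid it is usually modest. It would be going too far to call the planned tests invalid or to expect age adjustment to remove all distortion. One exploratory objective is affected; the prevalence estimate is not.

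**What to change.** In section 5.10:

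- Keep the chi-square tables as crude description, with Fisher's exact test where an expected count is below 5.
- For each risk factor, add the crude OR and an age-adjusted OR, each with a 95% CI, on data pooled over hospitals. Use logistic regression with age, Firth-penalised if events are few.
- Show results by age group.
- State that the results are exploratory, and that age adjustment does not remove the selection created in section 5.3 by requiring under-50s to hold at least one listed factor, to the extent that the requirement restricts entry.
- Present abnormal liver tests or liver disease, and cryoglobulinemia, as possible consequences of HCV, and do not use them as adjustment variables. Section 2 itself says that untreated infection "can progress to liver cirrhosis, hepatocellular carcinoma, and death related to these and other hepatic or extrahepatic problems", and reports that cryoglobulinemic vasculitis improves after HCV is eradicated.

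The cost is plan wording and a little more Stata code; age is already recorded, so no new data are needed. The downside is wide intervals. In the simulations, a factor held by about 15% had a median SE of the log OR of 0.29 to 0.47. Since exp(1.96 × 0.29) = 1.8 and exp(1.96 × 0.47) = 2.5, a 95% CI runs about 1.8- to 2.5-fold either way, and wider for rarer factors.
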